### Flow Diagram

We will report the number of eligible and recruited centers, and the corresponding patients included in the analyses by the allocation group in a flow diagram (Figure 1 in the Supplemental Material).

### Withdrawal and Loss to Follow-up

No centers withdrew from the study during the trial period. One dialysis center closed, and patients assigned to this center before it closed will continue to be followed up for the trial period. In addition, one center divided into two centers after the trial started; these centers will be treated as a single cluster for the primary intent-to-treat analysis. Given that patient follow-up is performed through provincial administrative health care data, the only reason for loss to follow-up is emigration from the province, which occurs at a rate of 0.5% per year for the general population; however, we can ascertain any outcomes that occur before emigration.

### Baseline Patient Characteristics

Baseline characteristics will be obtained through administrative data and center-level survey reporting. A list of baseline characteristics and database sources is available in appendix 7 of [name] et al. Continuous data will be summarized using means (standard deviations) or medians (25th, 75th percentiles) as appropriate. Binary and categorical variables will be summarized using counts and percentages. We expect to report a key set of baseline characteristics in the primary paper, with additional characteristics provided in an appendix.

We will use the Registered Persons Database supplied from the Ontario Ministry of Health and Long-term Care and enriched with other data sources at ICES to obtain demographic information. Kidney characteristics will be obtained from ORRS and the Canadian Organ Replacement Registry. Baseline outpatient medication dispensing will be obtained through the Ontario Drug Benefit (ODB) database using a 120-day lookback before the index date. Health care use in the year before the index date and baseline characteristics in

the 5 years before the index date will be assessed using the Ontario Health Insurance Plan Claims Database (OHIP), the Canadian Institute for Health Information Discharge Abstract Database (CIHI-DAD), CIHI's Same Day Surgery database, and the National Ambulatory Care Reporting System database. The OHIP Claims Database is supplemented with the ICES Physician Database and the Corporate Provider Database to obtain data on health care use with specific provider types. Long-term care status will be obtained from ODB, OHIP, and the Continuing Care Reporting System. Baseline laboratory information in the year before the index date will be obtained through the Ontario Laboratories Information System. We will use ICES-derived cohorts to determine the history of certain chronic conditions such as diabetes, congestive heart failure, hypertension, and chronic obstructive pulmonary disease. Whenever possible, we will use validated algorithms to define baseline variables that have been used in multiple prior studies.

### Analysis

#### Outcome Definitions

The *primary outcome* is a composite of cardiovascular-related death or hospital admission with myocardial infarction, congestive heart failure, or ischemic stroke. Cardiovascular-related hospitalization will be defined using main diagnostic codes from CIHI-DAD. Data on cause of death will be obtained from the ORGD, which uses a modified version of Becker's groupings based on *International Classification of Diseases 10th Revision (ICD-10)* coding. The specific algorithm for the primary composite outcome is provided in the trial protocol.

The *key secondary outcome* is the mean drop in intradialytic systolic blood pressure. To calculate this, we will subtract each patient's nadir intradialytic systolic blood pressure from their predialysis systolic blood pressure, and then average these values at the center level for each of the 48 timepoints during the 4-year trial period. As described in section "Timing of Outcome Assessments" above, anonymized data on patients' predialysis systolic blood pressure and their intradialytic systolic blood pressure were collected from a random sample of 15 patients at monthly intervals from each dialysis center. These blood pressure data will be averaged monthly for each center. As such, during the 4-year trial period, we will have a total of 48 summary measures (ie, 1 a month), for each of the 84 centers in our trial.

The *other secondary outcomes* are a composite of all-cause mortality or cardiovascular-related hospitalization, all cause-mortality, and the components of the primary outcome examined separately: hospital admission with myocardial infarction, hospital admission with congestive heart failure, hospital admission with ischemic stroke, and cardiovascular-related mortality.

We will also examine a composite of all-cause emergency room visits or all-cause hospitalizations (each will also be examined separately as the number of visits and hospitalizations, respectively), a hospital encounter with lower limb amputation, and a hospital encounter with a major fall or fracture.

Finally, we will examine four definitions of intradialytic hypotension using the same blood pressure data as for the key secondary outcome at the cluster level. We will examine the center's proportion of patients (weighted by the dialysis center size) whose (1) systolic blood pressure dropped from  $\geq 90$  mm Hg before dialysis to  $< 90$  mm Hg during dialysis; (2) nadir intradialytic systolic blood pressure was  $\geq 25\%$  lower than their predialysis level or whose systolic blood pressure dropped from  $\geq 90$  mm Hg before dialysis to  $< 90$  mm Hg during dialysis; (3) nadir intradialytic systolic blood pressure was  $\geq 25\%$  lower than their predialysis level; and (4) nadir intradialytic systolic blood pressure was  $\geq 35$  mm Hg lower than their predialysis level.

### Analytic Methods

For both the intervention and control groups, we will summarize the weighted proportion of the patients' observation time spent receiving hemodialysis at an index center (or a center providing the same allocated temperature protocol as the index center), the time spent receiving hemodialysis at other centers, and the time spent receiving other forms of kidney replacement therapy (as described in the "Adherence and Protocol Deviations" section, above, and in Figure 2 in the Supplemental Material). Patient crossovers between the intervention and control arms will also be reported.

**Analysis of the primary outcome.** The primary analysis will follow an intention-to-treat approach. Eligible patients will be analyzed according to their index center's treatment allocation (regardless of whether they transitioned to other dialysis centers or received other types of kidney replacement therapy in follow-up). Patients will be followed up until they experience the primary outcome, emigrate from Ontario, or die of a noncardiovascular cause (which will be treated as a competing-risk event).

We will report the crude frequency (%) and crude event rate (number of events per 100 person-years) for the time to first event for the primary composite outcome. We will create a graph of the nonparametric cumulative incidence function (CIF) showing the time followed, number of events, and patients at risk during regular intervals in the trial for the intervention and control groups. Noncardiovascular death will be treated as a competing-risk event. We will present the curves for visualization purposes only (no statistical tests will be conducted for differences between curves); we will simultaneously present the curves of the primary outcome, the components of the composite outcome, and the competing risk of noncardiovascular death.

We will assess the intervention's effect on the rate of the primary outcome using the multivariable generalized-estimating-equations extension for the Fine and Gray's subdistribution proportional hazards, with an exchangeable covariance matrix, to account for the clustering of patients within hemodialysis centers and the competing risk of noncardiovascular death. We will supplement the primary analysis with the cause-specific hazard model for both the primary outcome and competing-risk of noncardiovascular death. We also will explore the composite of our primary event with the competing risk as described in the "Additional Analyses" section below.

As our study used covariate-constrained randomization, we will adjust for constrained covariates in our analyses; these patient-level covariates include age, biological sex, rural status, race, modified Charlson comorbidity index, number of unique hospital admissions (in the 12 months before the index date), number of unique hypertensive prescriptions, referral to a nephrologist  $< 3$  months before initiating dialysis, type of vascular access on the index date, serum albumin on the index date, and the following baseline comorbidities: myocardial infarction, congestive heart failure, peripheral vascular disease, and diabetes mellitus. We will also adjust for the cluster-level historical rate of the composite outcome of cardiovascular-related death and major cardiovascular-related hospitalization.

We will evaluate and report the model assumptions for the clustered subdistribution hazard and cause-specific hazards models. Appropriate techniques will be applied when model assumptions are violated. Specifically, this model assumes a linear relationship between the log hazard and covariates. We will assess the assumption for linearity using residual plots. From historic data, we expect that the linearity assumption will be violated for our continuous covariates. If this occurs, we plan to correct for the nonlinear covariates using restricted cubic splines. We will assess the proportionality of the hazard visually and use the Schoenfeld test for the intervention. If the assumption of proportionality is violated, we will consider alternative methods so that the model remains valid (ie, a time-stratified model to identify constant hazard ratios within appropriate time intervals).

If we observe a statistically significant effect of the intervention on the rate of the primary outcome, we will provide the absolute risk difference (and 95% CI) of the CIF for the intervention and control groups at different time points during follow-up (including the median time points).

**Bayesian analysis of the primary outcome.** Our trial is powered to detect a hazard rate reduction in the primary composite outcome of at least 20% (corresponding to a hazard ratio of 0.80). We acknowledge that effects smaller than 20% could still be clinically meaningful. While we will give precedence to the results of the frequentist analysis, we will additionally conduct a prespecified Bayesian analysis to examine the probability that the intervention reduces the rate of the primary composite outcome by 5%, 10%, and 15% compared with the control

group based on the trial results. This analysis is motivated by advice that prespecified Bayesian analyses can complement frequentist analyses in the interpretation of the results of randomized clinical trials.

We will conduct and report a Bayesian analysis based on existing guidelines. We aim to determine the probability that the intervention (1) affects the primary outcome and (2) reduces the hazard rate of the primary outcome by 5% to 30%, given the observed data. The range of hazard ratios will be presented in a figure. We considered a minimum 5% hazard rate reduction (ie, hazard ratio = 0.95) in the primary composite outcome as clinically relevant, as adopting the intervention with such an effect would still prevent many major cardiovascular-related hospitalizations and/or deaths each year.

We will explore a range of prior distributions (see Appendix 1 and Table 1 in the Supplemental Material) that can condition the posterior distribution. We will use priors to reflect varying degrees of enthusiasm and skepticism for the benefit of a personalized temperature-reduced dialysate before starting MyTEMP. The parameter's estimate and standard errors will be obtained from the analysis (as described in the "Analysis of the primary outcome" section above) and combined with prior distributions to obtain the model's posterior distributions. We will estimate the Bayes factor and credible intervals using Markov chain Monte Carlo sampling techniques with at least 3 parallel chains. We will report the probability of the truth of our conclusions. This approach enables the specification of prior information, controls the sampling, and obtains posterior summary statistics and convergence diagnostics. The convergence of the generated Markov chain will be assessed by examining the trace plot, autocorrelation function plot, and posterior density plot.

**Analysis of the key secondary outcome.** The between-group difference in the key secondary outcome (the mean drop in patients' intradialytic systolic blood pressure) will be obtained using an unadjusted, generalized linear mixed model on the cluster-period summaries that accounts for the repeated measurements at the cluster level over time using longitudinal analysis methods, and appropriate CIs will be generated as described in section "Confidence Intervals and *P* Values: Level of Statistical Significance" in the "Statistical Principles" section above.

**Analysis of other secondary outcomes.** We will use the same analytic approach as for the primary outcome to examine each component of the primary outcome separately and the other secondary time-to-event outcomes (ie, see secondary outcomes listed in "Confidence Intervals and *P* Values: Level of Statistical Significance" and "Outcome Definitions" sections). Death (or noncardiovascular-related death) will be treated as a competing-risk event in these analyses when not part of the outcome. The model assumptions will be assessed as described in the "Analysis of the primary outcome" section, above.

The number of all-cause hospital admissions and emergency department visits during the study period will be analyzed using a negative binomial model relevant for count data while adjusting for clustering of dialysis centers with generalized estimating equations and using the log of time as an offset. We have chosen a negative binomial model because the historic data show a propensity for overdispersion (ie, the mean and variance of all-cause hospitalization and emergency room visits appear to be different). We will assess model assumptions and evaluate the fit of our model. From historic data, we expect that 85% of our cohort will have at least 1 hospital admission and/or emergency department visit in follow-up, and we also expect this outcome to be right skewed. We will perform and report model diagnostics.

The four definitions of intradialytic hypotension will be analyzed at the center level in a similar manner as the key secondary outcome (ie, unadjusted, generalized linear mixed model on the cluster-period summaries).

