**Analysis of the primary outcome.** Our analyses will account for the design and covariate-constrained randomization. In the primary intention-to-treat analyses, we will also assess the effect of the intervention on the rate of the composite outcome of cardiovascular-related death or hospitalization using the multivariable generalized-estimating-equations extension for the Cox proportional hazard model, with an exchangeable covariance matrix, to account for the clustering of individuals within hemodialysis centers. Patients will be censored at end of study follow-up or earlier if they die due to a non-cardiovascular-related cause. Patients who recover renal function, switch to a hemodialysis center with the alternative or no temperature allocation, receive a kidney transplant, or switch to home dialysis will be followed for outcomes according to their initial random allocation (see “Additional Exploratory Analyses” section).

**Analysis of secondary outcomes.** Between-group mean differences in the drop of mean systolic blood pressure is the key secondary outcome, because it examines the mechanism through which a lower dialysate temperature is expected to improve outcomes. This outcome will be analyzed at the center level using a repeated-measures random-effects linear mixed model. This model will provide an estimate (with 99% confidence intervals—see “Statistical Significance” section) of the absolute mean difference in the intradialytic drop in systolic blood pressure between the 2 groups.

For the analysis of the other secondary outcomes, the same approach described for the primary outcome will be used to analyze each component individually (eg, cardiovascular-related death, hospital admission with myocardial infarction) and the other secondary time-to-event composite outcomes (ie, all-cause mortality or cardiovascular-related hospitalization). Noncardiac death (except for outcomes that include all-cause mortality) will be treated as censoring events in these analyses. Model fit will be assessed to ensure

that all assumptions are met (eg, proportional hazards). If proportional hazard assumption is violated, we will explore using a time-stratified Cox model.

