### Statistical Significance

In keeping with recommended practice, our aim is to avoid type I errors due to multiple comparisons. We will use the parallel gatekeeping procedure to control the overall family-wise error rate at 0.05. The first family of hypotheses includes both the primary and key secondary hypotheses (composite primary outcome and drop in intradialytic systolic blood pressure), with weights of 0.8 and 0.2, respectively. If the intervention improves at least 1 of the 2 outcomes in the first family of hypotheses, outcomes in a second family of hypotheses will be tested in the following order at a level of significance that maintains the overall error rate across all prior testing at .05: all-cause mortality or cardiovascular-related hospitalization, all-cause mortality, hospital admission with myocardial infarction, hospital admission with congestive heart failure, and hospital admission with ischemic stroke. Any reported confidence intervals that maintain the family-wise error rate at .05 will be adjusted for the tested level of significance.

The reporting of treatment effects on outcomes including secondary outcomes examined after the family-wise error rate exceeds 0.05, additional outcomes, prespecified and post hoc subgroup analyses, and exploratory analyses will be limited to point estimates with 95% confidence intervals (without *P* values), and we will indicate that these interval widths are not adjusted for multiple testing, so that inferences drawn from them may not be reproducible.

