## Statistical Principles

### Confidence Intervals and *P* Values: Level of Statistical Significance

We planned the trial using a parallel gatekeeping procedure to control the overall error rate at 0.05 (to control for multiple testing). The 2-sided significance level will be 0.04 for the primary hypothesis and 0.01 for the key secondary hypothesis.

The remaining secondary outcomes will be tested as follows: If the overall error rate for the primary hypothesis and key secondary hypothesis exceeds 0.05, the results of subsequent tests will be provided as point estimates with 95% confidence intervals (CIs; without *P* values), and we will indicate that the interval widths are not adjusted for multiple testing and that the inferences may not be reproducible.

If there is a statistically significant improvement in the primary outcome or the key secondary outcome, the remaining secondary outcomes will be tested in the following order at a level of significance that maintains the overall error rate across all prior testing at 0.05 (example below): (1) A composite of all-cause mortality or cardiovascular-related hospitalization, (2) all-cause mortality, (3) hospital admission with myocardial infarction, (4) hospital admission with congestive heart failure, (5) hospital admission with ischemic stroke, and (6) cardiovascular death.

For example, if the primary outcome is nonsignificant ( $P \geq .04$ ) and the key secondary outcome is nonsignificant ( $P \geq .01$ ), no further hypothesis testing will be performed. If the primary outcome is significant and the key secondary outcome is nonsignificant, then the remaining secondary outcomes will be tested at a significance level of 0.04 until a *P* value is  $\geq .04$ . If the primary outcome is nonsignificant and the key secondary outcome is significant, then the remaining secondary outcomes will be tested at a significance level of 0.01 until a *P* value is  $\geq .01$ . Once one of these tests exceeds an overall error rate across all prior testing at 0.05, as described above, the results of subsequent analyses will be limited to point estimates with 95% CIs (without *P* values), and we will indicate that the interval widths are not adjusted for multiple testing and that the inferences may not be reproducible.

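### The between-arm absolute risk difference for the primary outcome, with its interval, is to be reported only if the primary test is significant; it should be reported whatever the result.

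*Combined protocol and SAP*

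**What the plan says.** The SAP, in Analysis of the primary outcome, makes the absolute comparison conditional: "If we observe a statistically significant effect of the intervention on the rate of the primary outcome, we will provide the absolute risk difference". The interval level is given in the same sentence: "we will provide the absolute risk difference (and 95% CI) of the CIF for the intervention and control groups". The difference is to be shown at several follow-up times. The only ones identified are median time points, and the plan does not say which median is meant. The later correction to the SAP leaves this sentence unchanged.

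Other absolute information does not depend on the test. The same section commits to per-arm summaries: "We will report the crude frequency (%) and crude event rate (number of events per 100 person-years) for the time to first event". It also plans cumulative incidence curves by arm, for display only and without a test between them.

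Three further statements bear on the interval level:

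- SAP, Confidence Intervals and P Values: "The 2-sided significance level will be 0.04 for the primary hypothesis and 0.01 for the key secondary hypothesis".
- Final protocol, Statistical Significance: "Any reported confidence intervals that maintain the family-wise error rate at .05 will be adjusted for the tested level of significance". For the key secondary outcome, tested at 0.01, the final protocol accordingly plans its estimate "with 99% confidence intervals".
- The same protocol section gives results outside the error-controlled sequence 95% intervals, on condition that "we will indicate that these interval widths are not adjusted for multiple testing".

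**The concern.** Whether an effect estimate is reported should not depend on its P value. Here the condition removes the interval for the absolute difference in the case where the reader most needs to know which absolute effects remain compatible with the data.

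That case is likely under the plan's own assumptions. The SAP regards a 5% hazard reduction as clinically relevant, and justifies this by the number of events it would prevent, which is an argument on the absolute scale. The final protocol concedes limited power below a 20% reduction. Effects the plan considers worthwhile would therefore often give a nonsignificant test and no absolute interval.

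A reader could not easily fill the gap from the per-arm percentages. A valid interval has to allow for clustering in 84 centers and for non-cardiovascular death, which the SAP supplement expects in 23% of patients.

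**Working it through.** **Inputs.** From the final protocol, Statistical Power and Appendix 11a: control hazard λ0 = 0.095 per person-year, coefficient of variation k = 0.216, harmonic mean y = 163 person-years per center, c = 42 centers per arm, two-sided α = 0.04, and 80% power at hazard ratio (HR) 0.80. From the SAP supplement, text to Figure 2: 21% of patients expected to have the primary outcome. I use 21% as the control-arm cumulative incidence, which is an assumption.

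**1. Reproduce the stated power.** With λ1 = 0.80 × 0.095 = 0.076,

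power = Φ( √[ (c−1)(λ0−λ1)² / {(λ0+λ1)/y + k²(λ0²+λ1²)} ] − 2.054 ).

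- Numerator: 41 × 0.019² = 0.014801.
- Denominator: 0.171/163 + 0.046656 × 0.014801 = 0.001049 + 0.000691 = 0.001740.
- Square root of the ratio: 2.917. Power = Φ(0.863) = 80.6%, against the stated 80%.

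**2. Implied standard error.** SE(log HR) = −ln(0.80)/(2.054 + 0.842) = 0.2231/2.895 = 0.077. At this SE, a significant benefit requires an estimated HR below exp(−2.054 × 0.0771) = 0.854.

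**3. How often the difference is withheld, and what is seen when it is not.** For each true HR, two million normal draws of log HR were made with this SE. Each was converted to a risk difference as 0.21 − (1 − 0.79^HR). Those with two-sided p < 0.04 were kept.

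| True HR | Not reported | True difference (points) | Mean reported difference (points) | Ratio |
|---|---|---|---|---|
| 0.80 | 20% | 3.8 | 4.2 | 1.10 |
| 0.85 | 48% | 2.8 | 3.8 | 1.33 |
| 0.90 | 75% | 1.9 | 3.5 | 1.86 |
| 0.95 | 91% | 0.9 | 3.1 | 3.28 |

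The plan's own tables agree. Appendix 11a, at CV 0.22 and rates of 0.09 to 0.10, gives 52% to 54% power at HR 0.85 and 25% to 26% at HR 0.90. That means nonreporting of 46% to 48% and 74% to 75%. The simulations in Appendix 11b give 56% power at HR 0.85, so 44% nonreporting.

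**4. Coverage among reported results.** At true HR 0.80, 0.85, 0.90 and 0.95, a 95% interval covers the truth in 96.9%, 95.2%, 89.8% and 66.9% of reported cases. A 96% interval covers in 97.5%, 96.2%, 91.8% and 72.8%. Without selection the 95% interval covers 95.0%. The shortfall at small effects comes from the selection, and a slightly wider interval does little about it.

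**5. Interval level.** 1.960/2.054 = 0.954, so the 95% interval is 4.6% narrower than the 96% interval. At HR 0.80, with control incidence treated as fixed, the SE of the difference is 0.79^0.80 × 0.2357 × 0.80 × 0.0771 = 1.20 points. The half-widths are then 2.36 points (95%) and 2.47 points (96%), a gap of about 0.11 points.

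**The case against.** The strongest reply is that little is hidden. Crude risks, crude rates and cumulative incidence curves are shown by arm in every case. The hazard ratio is not subject to the condition. The SAP sets its 5% relevance threshold on the hazard scale, so the hazard-ratio interval and the prespecified Bayesian analysis address it directly, whatever the primary P value. All of this stands. It limits the point to the between-arm absolute difference and its interval, which none of those items supplies.

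Second, the condition does not alter the number a significant trial would report. That also stands. The ratios in the table describe the average over trials that report. Removing the condition does not shrink an estimate in any one significant trial; it ensures that the nonsignificant trials report theirs too.

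Third, a reader might infer that the 95% interval is too narrow, or that it breaks the plan's multiplicity rule. The documents do not support this. A 95% interval is valid at its own label. The risk difference is not in the SAP's list of tested outcomes, and the protocol allows 95% intervals outside the tested sequence if they are marked as unadjusted. A 95% interval could disagree with the test only when 0.04 ≤ p < 0.05 (if both rest on the same model), and under the present rule no difference is reported then. What remains is that the SAP does not say which interval rule governs this quantity and attaches no label.

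**Conclusion.** The point holds as a matter of result-dependent reporting. The only planned between-arm absolute estimate with an interval for the primary outcome is withheld unless the primary test is significant. That would happen in about one trial in five at the design effect (HR 0.80), about half at HR 0.85, three quarters at HR 0.90 and nine in ten at HR 0.95, the smallest effect the plan calls relevant.

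The primary test, the hazard ratio and the control of type I error are not affected. It would be wrong to read this as suppression of all absolute information or as an error in the 95% interval. The interval level is a minor matter of consistency.

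The figures assume a normally distributed log hazard ratio with the SE of 0.077 implied by the stated power, the same SE at every true HR. The risk-difference figures also assume a control-arm cumulative incidence of 21%. The documents state neither the SE nor that control-arm figure. The nonreporting percentages at HR 0.85 and 0.90 are close to what the protocol's own power tables imply.

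**What to change.** In Analysis of the primary outcome, delete the condition and commit to the following, whatever the primary P value:

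- Report the between-arm difference in cumulative incidence with an interval that allows for clustering by center, and name the method (resampling whole centers within arm would be one option).
- Name the time points in advance, for example 1, 2 and 3 years from the index date plus the planned median time points, with the median defined. A 4-year point should not be used: observation starts no earlier than April 3, 2017 and ends on March 31, 2021, a few days short of 4 years.
- State the interval level: either 96%, to match the 0.04 test under the protocol's rule, or 95% with an explicit note that it is not adjusted for multiplicity.

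The cost is a sentence or two in the SAP and a small addition to the analysis. The cumulative incidence functions are already planned, and no new data are needed.
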